17.3. ECG EVALUATIONS

Results from the central Electrocardiogram (ECG) Reading Centre will be included in the reporting of this study.

The following ECG parameters will be reported for this study:

- PR Interval (msec)

- QRS Interval (msec)
- QT Interval (msec)
- QTcF Interval (msec)
- QTcB Interval (msec)
- Heart Rate (beats per minute [bpm])
- Overall assessment of ECG (Investigator’s judgment):
 - Normal
 - Abnormal, Not Clinically Significant (ANCS)
 - Abnormal, Clinically Significant (ACS)

On Day 1, prior to dosing, triplicate ECGs must be performed. Triplicate results will be used in the summaries by taking an average of the 3 results. The average of the 3 results will be the baseline. Baseline for the investigator’s judgement will be the mode judgment of the 3 results. In the case of multiple modes, the mode with the worst-case judgment (Normal<ANCS<ACS) will be used as baseline.

If only 2 ECG measurements instead of triplicate on Day 1 pre-dose, take average of the two; if only 1 measurement then this will be the baseline.

The handling of re-test and unscheduled measurements is detailed in section 6.3of the SAP.

If there were more measurements on a scheduled visit, choose measurement as follows:

1. Choose first triplicate, if more than one done.
2. If done on Day 1, ensure you choose measurement that it is prior to dosing.
3. If there are more than 1 ECG measurements, choose the scheduled one where interpretation of the measurement from the vendor data is not "UNABLE TO EVALUATE" .
 - a. If pre-dose/post-dose and interpretation of the measurement from the vendor data is "UNABLE TO EVALUATE" and no further pre-dose/post-dose unscheduled visits on the same day, respectively – set to missing
 - b. If pre-dose/post-dose and interpretation of the measurement from the vendor data is "UNABLE TO EVALUATE" and there is another unscheduled pre-dose/post-dose – choose next unscheduled visit on the same day

The following summaries will be provided for ECG data:

- Actual and change from baseline by visit (for quantitative measurements)
- Shift table representing changes from Normal, ANCS and ACS, using Investigator’s judgement
- Incidence of markedly abnormal criteria

- Listing of patients meeting markedly abnormal criteria

17.3.1. ECG MARKEDLY ABNORMAL CRITERIA

Markedly abnormal quantitative ECG measurements will be identified in accordance with the following predefined markedly abnormal criteria:

- Absolute values for QT interval, QTcB interval and QTcF interval will be classified as:
 - > 450 msec
 - > 480 msec
 - > 500 msec
- Change from Baseline for QT interval, QTcB interval and QTcF will be classified as:
 - >30 msec increase from baseline
 - >60 msec increase from baseline

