8.4.1 Vital Signs

- Vital signs should be obtained prior to blinded study medication dosing at all visits.
- Temperature in Celsius, pulse rate, blood pressure, and respiratory rate will be assessed. The mode of temperature collection should be noted in the source (e.g. oral, forehead, etc).
- Blood pressure and pulse measurements will be assessed with a completely automated device. Manual techniques will be used only if an automated device is not available.
- Supine blood pressure, respiratory rate, and pulse measurements should be obtained after the patient has been at rest for at least 5 minutes in the supine position and located in a quiet setting without distractions (eg, television, cell phones).

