9.4.2 Safety Analyses

Safety analysis will be based on the safety set.

Adverse events will be analyzed using quantitative and qualitative measures. Treatment-emergent adverse events will be summarized by treatment group for all AEs, related AEs, serious adverse events, deaths, adverse events leading to discontinuation of blinded study medication or to withdrawal from study, adverse events of different severity and adverse events of different chronicity. Treatment-emergent adverse events will be coded using the Medical Dictionary for Regulatory Activities (MedDRA) and summarized by system organ class and preferred term for each treatment group. For selected adverse events, time to first event will be visualized using Kaplan-Meier plots.

Laboratory data will be summarized by each visit including change from baseline. The number of normal, abnormal not clinically significant and abnormal clinically significant values on each parameter will be summarized for change over study using shift tables. All data will be listed and values outside reference ranges will be highlighted in the listings.

Vital signs and continuous parameters from the ECGs will be summarized by each visit including change from baseline. Values outside pre-specified ranges (low, high) or changes exceeding pre-specified limits will be summarized by visit for each parameter. The number of normal, abnormal not clinically significant and abnormal clinically significant values on the ECG overall evaluation will be summarized for change over study using shift tables. All data will be listed and values outside reference ranges will be highlighted in the listings.

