11.5 Appendix 5: ECG Withdrawal Criteria

All ECGs conducted or overread after a patient has been randomized will be subject to ECG Withdrawal Criteria (including the pre-dose ECGs at Visit 1 and subsequent visits). A patient may be withdrawn from study medication if the 12-lead ECG recording during the study shows any of the following abnormalities:

The Investigator may withdraw patients from study treatment for any other clinically significant finding (Section 7.0). Triplicate ECGs (over a brief period of time) should be performed on patients experiencing any of the following or a clinically significant abnormality on their ECG per the Investigator's discretion, in order to confirm the abnormality in 2 of 3 measurements. The decision to withdraw a patient should also take into consideration the patient's medical history and prior/baseline ECGs.

- Sinus tachycardia ≥ 120 bpm (Sinus tachycardia ≥ 120 bpm should be confirmed by 2 additional readings at least 5 minutes apart).
- Sinus bradycardia < 37 bpm (Sinus bradycardia < 37 bpm should be confirmed by 2 additional readings at least 5 minutes apart).
- Increase in heart rate ≥ 40 bpm relative to baseline.
- Multifocal atrial tachycardia
- Supraventricular tachycardia (> 100 bpm)
- Atrial fibrillation with rapid ventricular response (rate > 120 bpm).
- Atrial flutter with rapid ventricular response (rate > 120 bpm).
- Ventricular tachycardia (non-sustained, sustained, polymorphic or monomorphic)
- Ventricular flutter
- Ventricular fibrillation
- Torsades de Pointes
- Evidence of Mobitz type II second degree or third degree atrioventricular (AV) block.
- AV dissociation
- 2:1 AV block
- Bifascicular Block (RBBB plus LAHB or RBBB plus LPHB)
- An increase in QTcF > 60 msec from baseline ECG
- Uncorrected QT > 600 msec
- For patients with QRS duration < 120 msec: QTc(F) ≥ 500 msec or an ECG that is unsuitable for QT measurements (e.g. poor defined termination of the T wave).
- For patients with QRS duration ≥ 120 msec: QTc(F) ≥ 530 msec or an ECG that is unsuitable for QT measurements (e.g. poor defined termination of the T wave).
- Myocardial infarction (acute or recent) Note: Evidence of an old resolved Myocardial infarction is not exclusionary.

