17.4.1. VITAL SIGNS MARKEDLY ABNORMAL CRITERIA

Markedly abnormal quantitative Vital Signs measurements will be identified in accordance with the predefined markedly abnormal criteria found in Table 5.

Markedly Abnormal Post-Baseline Vital Sigs

Variable	Unit	Abnormally Low	Abnormally High
SBP	mmHg	- A decrease from Baseline of ≥ 40 - Value ≤ 90	- An increase from Baseline of ≥ 40 - Value ≥ 180
DBP	mmHg	- A decrease from Baseline of ≥ 20 - Value ≤ 50	- An increase from Baseline of ≥ 20 - Value ≥ 105
Pulse rate	Bpm	- A decrease from Baseline of ≥ 30 - Value ≤ 50	- An increase from Baseline of ≥ 30 - Value ≥ 110

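### ECG heart rate 1.5 hours after dosing, like PR and QRS, has no pre-specified outlier count by arm, although the protocol plans such summaries for each continuous ECG parameter

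*SAP*

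**What the plan says.** Protocol 9.4.2 takes vital signs and ECG together: "Vital signs and continuous parameters from the ECGs will be summarized by each visit including change from baseline". Its next sentence adds the outlier summary: "Values outside pre-specified ranges (low, high) or changes exceeding pre-specified limits will be summarized by visit for each parameter".

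SAP 17.3 names the ECG parameters to be reported: PR, QRS, QT, QTcF, QTcB and "Heart Rate (beats per minute [bpm"]). It plans observed values and changes at each visit, a shift table of the investigator's overall assessment, and both an incidence table and a patient listing based on markedly abnormal criteria. SAP 17.3.1 defines those criteria. For absolute values: "Absolute values for QT interval, QTcB interval and QTcF interval will be classified as" above 450, 480 or 500 msec. For change: "Change from Baseline for QT interval, QTcB interval and QTcF will be classified as" above 30 or 60 msec. Heart rate, PR and QRS have no entry.

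The SAP's only heart-rate limits are for pulse, in 17.4.1. The high criteria are "An increase from Baseline of ≥ 30 - Value ≥ 110" bpm; the low criteria are a fall of at least 30 bpm or a value of at most 50 bpm. Protocol 8.4.1 fixes when pulse is measured: "Vital signs should be obtained prior to blinded study medication dosing at all visits".

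The Schedule of Activities (Protocol 1.3) places a 1.5-hour post-dose ECG at Day 1 and Weeks 6, 12 and 24, and at early termination. Protocol Appendix 5 (11.5) includes "Increase in heart rate ≥ 40 bpm relative to baseline" among its ECG withdrawal criteria.

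**The concern.** The protocol's sentence on outliers reaches every continuous ECG parameter, yet the SAP supplies limits for three of the six it lists. The list of changes in SAP 3.3 records items as small as dropping adverse-event chronicity, but not this one. A reader of the SAP would not know that anything had been narrowed.

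Heart rate is the parameter where this matters most. The pulse table might seem to cover it, but pulse is taken before the morning dose. The one scheduled look at heart rate after a dose is the 1.5-hour ECG, and nothing in the SAP counts how many patients in each arm crossed a limit there. Heart rate is also the one exception named in Protocol 4.3 when it reports no ECG or vital-sign changes at any dose, and Protocol 2.3 describes that effect as transient and as a change in peak heart rate. A count taken only before dosing is poorly placed to pick up an effect of that kind.

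**Working it through.** **Parameters against limits**

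| Parameter | When measured | Outlier limits in SAP |
|---|---|---|
| QT, QTcB, QTcF | ECG pre-dose and 1.5 h post-dose | Yes (17.3.1) |
| ECG heart rate | ECG pre-dose and 1.5 h post-dose | None |
| PR, QRS | ECG pre-dose and 1.5 h post-dose | None |
| Pulse | Vital signs, pre-dose only | Yes (17.4.1) |

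**What the pulse table sees.** On Day 1 the pulse precedes the first dose, so it is a baseline value. At Weeks 6, 12 and 24 the morning dose is withheld until the clinic, and Protocol 1.4 times pre-dose spirometry at 11.5 to 12 hours after the evening dose. Pulse, also taken before that dose, is close to trough.

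**How many readings are involved.** 4 scheduled post-dose ECGs × about 800 patients = about 3,200 readings, of which 4 × 500 = 2,000 are on ensifentrine. This is a ceiling before dropout. It is a number of measurements, not of missed events.

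**Whether the mean can stand in for a count.** This illustration uses the planned arms of 500 and 300 (Protocol 9.2). The outlier shares, sizes of rise and SD are assumptions; the documents give none of them.

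Shift in the ensifentrine mean = share of patients × excess rise:

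- 1% (5 patients) × 30 to 40 bpm = 0.3 to 0.4 bpm
- 2% (10 patients) × 30 to 40 bpm = 0.6 to 0.8 bpm
- 4% (20 patients) × 30 to 40 bpm = 1.2 to 1.6 bpm

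95% CI half-width for the difference in means = 1.96 × SD × √(1/500 + 1/300) = 1.96 × SD × 0.0730:

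- SD 8 bpm: 1.1 bpm
- SD 12 bpm: 1.7 bpm

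At 1% or 2%, the shift is smaller than the half-width for either SD. At 4% the two are of similar size. The mean would not reliably show such a group.

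**Whether the maximum can.** SAP 6.5 makes minimum and maximum part of the default summary, so one large rise would be visible as the maximum change. But 5 patients and 20 patients with rises of up to 40 bpm can give the same maximum. It shows that a large rise occurred, not how often.

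**Whether the time point is clear.** SAP 17.3 does not say that by-visit ECG summaries or incidence counts are split into pre-dose and 1.5 hours post-dose. Its rule for choosing among several ECGs at a visit asks for a pre-dose measurement on Day 1, which could be read as leaving out the first-dose 1.5-hour ECG.

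**The case against.** The strongest reply is that little is actually lost.

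- Post-dose heart rate is summarised by visit with minimum and maximum, and Protocol 9.4.2 has all data listed with out-of-range values highlighted.
- The shift table of normal and abnormal ECG assessments is a count, though not specific to heart rate.
- A clinically significant ECG abnormality meets the adverse-event definition and is tabulated. Post-randomization ECGs are also checked against Appendix 5.
- Safety analysis is descriptive, and no efficacy conclusion depends on it.

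All of this stands. A reader might infer that post-dose tachycardia would go unseen; the documents do not support that. What is missing is a between-arm incidence, mainly for rises that the investigator judged not clinically significant.

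A second reply concerns the signal. Protocol 2.3 reports mean rises of up to 12 bpm in healthy volunteers at 6 mg, and 3 bpm in peak heart rate in COPD at 6 mg twice daily only. This trial studies 3 mg, and Protocol 8.7.6 names no adverse events of special interest. That also stands. The documents do not show a heart-rate signal at the studied dose.

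Third, Protocol 9.4.2 refers to pre-specified limits without saying that each parameter must have one, so calling it a firm promise of limits for every ECG parameter goes beyond the text. Even so, its plain sense is a summary for each parameter, and a parameter without limits cannot have one.

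Last, the output shells are not part of the documents and might contain such a table. SAP 17.3.1 is nevertheless the only place where ECG criteria are defined.

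**Conclusion.** The point holds as a gap in descriptive safety reporting and an undeclared narrowing from protocol to SAP. ECG heart rate, PR and QRS have no pre-specified limits, and the pulse limits do not fill the gap for heart rate because pulse is taken before dosing. The consequence is the absence of a count by arm at the only scheduled post-dose heart-rate measurement, not the loss of the data.

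The figure of about 3,200 readings should not be taken as the size of an effect; the documents give no basis for saying how many outliers there would be. The conclusion that means are a poor substitute rests on the assumed shares, rises and SDs. The textual mismatch rests on no assumption beyond reading Protocol 9.4.2 in its plain sense and taking SAP 17.3.1 as the full set of ECG criteria.

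**What to change.** - Add ECG heart rate to SAP 17.3.1, using the pulse limits already in 17.4.1: value at least 110 or at most 50 bpm, and a rise or fall from baseline of at least 30 bpm. One shared set lets the ECG and pulse tables be read together.
- Optionally also count rises of at least 40 bpm, the change listed in Appendix 5. The Appendix 5 sinus tachycardia value of 120 bpm is less suitable as a cut-off for a single reading, because it is a rhythm finding to be confirmed by two further readings.
- Report by arm and visit, separately for pre-dose and 1.5 hours post-dose, and state that the Day 1 selection rule in SAP 17.3 does not remove the 1.5-hour ECG.
- For PR and QRS, either set limits or declare and justify their omission in SAP 3.3.

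These are reporting categories only and alter no withdrawal rule. The data are already collected, so the cost is a few extra rows in an existing table and a short SAP edit.

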17.4. VITAL SIGNS

[figure not shown]
The following Vital Signs measurements will be reported for this study:

- Supine Systolic Blood Pressure (mmHg)
- Supine Diastolic Blood Pressure (mmHg)
- Supine Pulse Rate (bpm)
- Respiratory Rate (breaths/min)
- Temperature (°C)
- Body weight (kg)
- Height (cm)
- BMI (kg/m²)

The following summaries will be provided for vital signs data (excluding respiratory rate, temperature, body weight, height and BMI):

- Actual and change from baseline by visit
- Incidence of markedly abnormal values
- Shift from baseline according to markedly abnormal criteria
- Listing of patients meeting markedly abnormal criteria

Respiratory rate, temperature, body weight, height and BMI will be listed.

17.4.1. VITAL SIGNS MARKEDLY ABNORMAL CRITERIA

Markedly abnormal quantitative Vital Signs measurements will be identified in accordance with the predefined markedly abnormal criteria found in Table 5.

Markedly Abnormal Post-Baseline Vital Sigs

Variable	Unit	Abnormally Low	Abnormally High
SBP	mmHg	- A decrease from Baseline of ≥ 40 - Value ≤ 90	- An increase from Baseline of ≥ 40 - Value ≥ 180
DBP	mmHg	- A decrease from Baseline of ≥ 20 - Value ≤ 50	- An increase from Baseline of ≥ 20 - Value ≥ 105
Pulse rate	Bpm	- A decrease from Baseline of ≥ 30 - Value ≤ 50	- An increase from Baseline of ≥ 30 - Value ≥ 110

17.5. COVID-19

From study initiation until 5Nov2021, patients with positive COVID-19 test indicating an active COVID-19 infection were withdrawn from the study.

A protocol clarification letter dated 5Nov2021 clarified that active infection includes known symptoms of COVID-19.

A protocol clarification letter dated 21Apr2022 clarified that active infection includes known lower respiratory symptoms of COVID-19.

Patients with discontinued due to COVID-19 will be summarized in the disposition table. Data collected on the “COVID-19 Visit Impact” eCRF page will be summarized by visit. Data on the optional COVID-19 testing will be listed.

17.6. PNEUMONIA

Pneumonia details recorded in the “Pneumonia” page of the eCRF will be listed.

17.7. EVALUATION INCLUDING EXCLUDED SITES

The following analyses will be performed on the Extended Safety Set:

- Summary of TEAEs
- TEAEs by SOC and PT
- Related TEAEs by SOC and PT
- Serious TEAEs by SOC and PT
- Markedly abnormal values for selected chemistry parameters
- Markedly abnormal values for vital signs
- Markedly abnormal values for ECG parameters

18. GENETIC ANALYSIS

Genotyping analyses (CYP2C9 and CYP2D6 phenotypes) will be completed as exploratory analysis by the sponsor and are not covered in this SAP.

19. BIOMARKER ANALYSIS

Assessment of Biomarkers (IL-6, IL-8 and C-Reactive Protein [CRP]) will be analyzed for the mITT using ANCOVA approach, as described in section 16.1.3 of the SAP at Weeks 12 and 24. Log transformation will be done on the data for the ANCOVA analysis. Values that are below limit of quantitation (LOQ) will be treated as LOQ/2 for analyses and summaries. Missing data will not be imputed. Biomarker data are blinded until after DBL.

20. PHARMACOKINETIC ANALYSIS

20.1. DEVIATIONS RELATED TO PK

Changes to the procedures or events, which may impact the quality of the pharmacokinetic (PK) data, will be considered important PDs for the purpose of inclusion of the affected results in the concentration summary. These changes or events will include any circumstances that will alter the evaluation of the PK. Examples include, but may not be limited to, an incomplete/inaccurate dose of ensifentrine inhaled and/or a prolonged interruption of nebulization (example due to prolonged coughing, etc.), sample handling/shipment/processing errors that lead to inaccurate bioanalytical results, and/or noncompliance in ensifentrine administration (inaccurate and/or incomplete dose administration). Interruption of nebulization

or spillage resulting in loss of more than 50% of dose will be evaluated on case-by-case basis to determine whether exclusion of ensifentrine results from analysis is warranted. Other changes to the procedures or events which do not impact the quality of the PK data will not be considered significant PDs. A common example of a non-significant PDs is a missed blood sample.

A general rule for handling of time deviations for the descriptive summary of the concentration data is provided below:

- If the most recent 2 prior doses were missed, then the pre-dose and postdose concentrations for the affected visit will not be included in the concentration summary.
- If the most recent prior dose was administered less than 6 hours prior or more than 18 hours prior to collection of the scheduled pre-dose sample (ie, the pre-dose sample is not collected within the window of 6 to 18 hours prior to the end of the inhalation of the last dose), the pre-dose concentration will not be summarized. Any post-dose concentrations scheduled for the affected visit will be included in the summaries.
- Samples scheduled to be paired with the 1.5-hour ECG collection will be summarized if they were collected within the window of ± 0.5 hours (relative to end of the inhalation).
- Pre-dose samples collected after start of the inhalation will be excluded from the summaries.
- Samples collected outside the allowable window specified in the protocol will not be summarized.
- ET/withdrawal results will be listed only as long as the patient has received at least 1 dose of ensifentrine.

Note: Sample collection records will be reviewed before or during final analysis to determine the extend loss of data records based on the above specifications. If the loss of records is considered to be unacceptable, the above windowing may be modified (widened) for inclusion of additional data in the concentration summary. Any decision to widen the acceptance criteria will be documented in the clinical study report.

A listing with patients or concentration results excluded from the summary statistics and the reasons for exclusion will be provided.

20.2. PHARMACOKINETICS DRUG CONCENTRATIONS IN PLASMA

Pharmacokinetic concentration outputs will be based on the PK set. Pharmacokinetic data will be blinded until after DBL. The observed drug concentrations will be listed and summarized by site (even / odd), as per schedule of Table 9 in the Protocol, and for each sampling time point by visit, using descriptive statistics (including N [sample size], n [available data], n < below lower limit of quantitation [BLQ], mean, SD, coefficient of variation [CV%], median, minimum, and maximum. Concentrations that are BLQ will be treated as zero for concentration

summaries. There will be no imputation of missing data.

A listing of PK blood sample collection times, derived sampling time deviations, and actual sample time will be also provided. Blood samples are to be collected as per schedule of Table 9 in Protocol. All PK concentrations will be listed with the same precision as the source data provided by the bioanalytical laboratory regardless of how many significant figures or decimal places the data carry.

For the reporting of descriptive statistics of PK concentrations, the mean and SD will be presented to 1 digit more precision than the source data. The minimum, median, and maximum will be presented to the same precision as the source data. CV% will always be reported to 1 decimal place. A minimum of n=3 is required for all descriptive statistics to be generated. If n is less than 3, only N, n, minimum, and maximum will be reported.

The concentration listing and summary will be described as appropriate in the clinical study report.

